# Data analysis

# **Refining Programme Theories**

Excel/word documents will be used to store data. The data collected from the recruited participants will be analysed collectively, using descriptive statistics where appropriate and inductively bringing together the various data sources in emerging themes. This will demonstrate how theories evolve in the course of the study. Engagement, involvement, and collaboration between each member of the research team will take place to refine theories to understand when, for whom and in what circumstances are two different types of compression bandages selected in clinical practice. It is hoped and expected that at the end of the study, new guidance for nursing staff will be developed to guide the selection of compression bandages.

# Duration of the project

Recruitment will take place over the course of 17 months, starting on the 1 December 2024 and ending on the 1 April 2026. First patient will be recruited on the 1 December 2024; last patient will be recruited on  $31^{st}$  January 2026.

# Definition of the end of the study

The end of the study is defined as the date of the final visit of the last patient participant.

# Ethics

This study is considered low risk for participants as compression bandages are commonly used in this patient population.

NHS Research Ethic Service (RES) review will be sought prior to the study commencement. HRA approval will be sought prior to study commencement. No other regulatory approvals will be required for this study.

# Funding

Milliken Healthcare Products, LLC has provided an unconditional grant for this study, worth £71,481.63. All compression bandages used in this study are standard care and will be purchased through the current procurement route.

Funding includes research nurse time; administrator time to facilitate site contracts and approvals and open access fees for rapid publication.

# Patient and Public Involvement

For the duration of this study, we will establish an 'Advisory Group' that will contribute to the management of the research. This group will comprise one or two patients; a district nurse; wound care nurse specialist (Tissue Viability) to monitor progress, provide guidance and help with problem-solving.

The research team will discuss issues as they arise with all or single members of the advisory Group.

# Safety

There is no anticipated personal safety risk associated with taking part in this study. Appropriate precautions are in place to ensure medical and personal information is kept safe through adhering to appropriate governance regulations.

Participants will be allocated compression bandages that are used for its intended licensed purpose, are considered standard care in the Trust and that are available via NHS procurement routes.

Apart from being allocated to a different type of compression bandage per leg, all patients will be commenced on a compression therapy; therefore, all patients will receive the indicated clinical care they would receive if they were not in the study; they will be cared for in exactly the same manner as they normally would bar that usually both legs would be compressed using the same product for ease of procurement. However, in standard care, it is not unusual to be prescribed two different brands of compression bandages. Some bandage types may be more comfortable at controlling symptoms such as pruritus.

Participants cannot claim payments, reimbursement of expenses or any other benefits or incentives for taking part in this research.

# Anticipated problems

The main risks associated with this study are with recruitment and they have been mitigated by working within one Trust (the Newcastle upon Tyne Hospitals NHS Foundation Trust).

#### Informed consent forms

Consent forms have been designed. We will be using an electronic tablet instead of a paper document and you will be asked to sign the consent form on the tablet.

An interpreter service will be used, if the patient has currently been using this service.

# Reporting of safety events and device complaints

This study involves the use of licensed Class I CE Mark post-market compression bandages currently used in standard practice and is not expected to pose additional medical risks to the patients beyond those of a routine clinical treatment.

Anticipated risks can be associated to misuse (e.g. poor compression bandage application techniques) and allergy to the bandages components.

In the very unlikely event that a Serious Adverse Event (SAE) has to be reported, a form has been devised. For the purpose of this study, a SAE has been defined as: an adverse event that led to death; led to a serious deterioration in the health of the subject, users, or other persons as defined by; either resulted in a life-threatening illness or injury, a permanent impairment of a body structure or a body function, or in-patient or prolonged hospitalisation, or medical or surgical intervention to prevent life-threatening illness or injury or permanent impairment to body structure or a body function; or led to foetal distress, foetal death or a congenital abnormality or birth defect.

Planned hospitalisation for a pre-existing condition, or a procedure required by the protocol without serious deterioration in health, is not considered a Serious Adverse Event.

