#### Sample and recruitment

#### a) Patient recruitment

40 patients will be recruited for having bilateral leg ulceration and being treated in compression bandages or being in compression bandages for the prevention of leg ulceration (re-)occurrence.

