# **Recruiting and Screening**

Patients will be existing patients on the Newcastle upon Tyne Hospitals NHS Foundation Trust District Nursing's workload. Potential patients participants will be identified using Systm1, the electronic documentation system used by District Nurses in Newcastle. A list of potential participants will be drawn by the administrative team within District Nurses.

During the course of standard care, District Nurses will ask permission for the Research Nurse to contact them via telephone, letter or email. With agreeing, the District Nurse will enter the following text in the patient electronic documentation: "Mr/Mrs/Ms [Patient name] has agreed for the Research Nurse to contact him/her regarding the ROSE study". Upon contact, the Research Nurse will give potential patient participants the PIS and seek informed consent.

Thus Nurse participants will be involved in the recruitment process, and it is hoped that this will enhance their willingness to be recruited to the study alongside their patients.

Nurse Participants will be contacted by the Research Nurse who is a NuTH employee, through the existing nursing management structure.

In accordance with Good Clinical Practice, participation in this study is voluntary and any decision not to participate will not have any impact on how the subject's clinical treatment is performed. Patients will have a minimum of 24h to decide whether to participate or until the following visit by the District Nurses team (compression bandages are changed 2-3 times per week).

Following recruitment, a participant will be considered enrolled once he/she signs and dates the informed consent form. Once enrolled, the participant will be assigned a unique subject number, which will not contain information that could identify him/her (such as name or date of birth). The unique participant number will be used to label study data throughout the study.

All District Nurses in the organisation will be sent the Patient Information Sheet by their managers so that they will be well informed about the study aim and objectives. The research nurse might observe the application of compression bandaging. Patients receive care by a group of District Nurses, it is not unusual for patients to see 10-12 different District Nurses during the course of their treatment. Nurse participation is voluntary.

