# Criteria for Withdrawal/Discontinuation/exit

- The duration of patient participation in the study is 8 weeks.
- Patient participation in the study will be terminated immediately in case of discomfort or intolerance to zinc or calamine or any allergen present in the dry bandages as per standard procedure.
- Each participant has the right to withdraw from the study at any time without prejudice.
   In addition, the investigator may advise that a participant be discontinued from the study at any time if the investigator considers it necessary for any reason; however withdrawal decisions remain with the participant at all times.
- The investigator may withdraw a subject at any time, for any reason.
- The reasons for withdrawal and discontinuation for any subject shall be recorded.
- Any data and information collected for the subject up until the time of withdrawal or discontinuation, may still be included in the study registry, unless the participant has asked that their data are not to be used. The site shall document all requests by participants regarding their data use.
- Where participants lose capacity to consent during their time in the study, they will be withdrawn from further follow up; however data collected until this point will be retained for use. No further data would be collected, or any other research procedures conducted in relation to the participant.

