# Compression bandage selection procedure

The choice to apply 'full compression' versus 'reduced compression' will be dictated by the aetiology of the ulcer, wound assessment etc as per standard care. However, one leg will be bandaged in 'paste' compression and one leg in 'dry' compression, through a process of randomisation, using pre-prepared sealed envelopes.

The two types of compression bandages that will be used in this study are 'standard care' and are:

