# Timeline

Each patient participant will be consented at time of recruitment. A patient information sheet will be offered. Each leg will be randomised to either  $S_1F/S_1R$ ,  $S_2F/S_2R$  or  $S_3F/S_3R$ . The Research Nurse will visit each patient participant where they receive their treatment at Week 0, Week 1, Week 4, and Week 8. All participants will have demographic data obtained and the following outcome measures (Table 1):

Weeks	0	1	4	8
Baseline measures (demographics, medical history, vascular history; nursing teams and setting)	~			
Visual analogue pain score (pre, during and after dressing change)	~	~	~	~
Visual analogue pruritus score	~	~	~	~
EQ-5D-5L	~			~
VEINES-QoL	~			~
Patient and Nurses Experience		
 
✓
 
	~	~
questionnaire				
Nurses technical questionnaire		✓	~	~
Photo(s) of both legs	~	✓	✓	✓

Table 1. Outcome measures

- a) Baseline measures (see Appendix 1)
- b) Visual analogue pain score (see Appendix 2)
- c) Visual analogue pruritus score (see Appendix 2)

- d) VEINES-QoL is a patient reported outcome measure score that focuses on lower limb health (see Appendix 2)
- e) EQ-5D-5L is a general quality of life measurement tool (see Appendix 2)
- f) Patient questionnaire for comfort at application, during wear and on removal, fluid handling (see Appendix 3).

During the recruitment process the research team will acts as a contact point and coordinator for patients requiring information and support. If concerns are raised on participants (mental) wellbeing based on the home visits or outcome of the assessments, referral of patients/families on to other professional agencies will be done as appropriate and according to the Trust guideline.

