# **APPENDIX 3. PATIENT AND NURSE'S EXPERIENCE** PATIENT AND NURSE QUESTIONNAIRE – CLINICAL EXPERIENCE

Bandage used: Right Leg S1F/S1R, S2F/S2R or S3F/ S3R (circle what applies)	S1F = UrgoK2 S1R = UrgoK2 Lite S2F = Coban2 S2R = Coban2 Lite S3F = AndoFlex TLC Calamine S3R = AndoFlex TLC Lite Zinc
FOR THE PATIENT TO COMPLETE	
Please rate the following as your overall experience of circle):	of wearing this bandage (please
Has this bandage helped with your pain?	Yes No N/a
Has this bandage improved your comfort?	Yes No N/a
Has this bandage improved your ability to wear normal footwear and clothes?	Yes No N/a
Has this bandage stayed in place?	Yes No N/a
Has this bandage improved your skin condition?	Yes No N/a
Has this bandage improved your skin irritation?	Yes No N/a
Please add any further comment of your personal experience	
FOR THE NURSE TO COMPLETE	
Prior to last bandage application, was the leg washed with Hydromol mixed in warm water?	Yes No N/a
Prior to last bandage application, was the leg debrided using a debridement cloth or tenatome?	Yes No N/a
Looking at the leg, has this bandage helped improve the leg's skin condition?	Yes No N/a
Looking at the leg, has this bandage reduced the leg's skin irritation?	Yes No N/a
Looking at the leg, has this bandage helped with wound healing?	Yes No N/a

Looking at the leg, has this bandage helped with wound

malodour?

Yes

No N/a

	S1F = UrgoK2
	S1R = UrgoK2 Lite
Bandage used: Left Leg	
	S2F = Coban2
S1F/S1R, S2F/S2R or S3F/ S3R (circle what applies)	S2R = Coban2 Lite
	S3F = AndoFlex TLC Calamine
	S3R = AndoFlex TLC Lite Zinc

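### Only serious adverse events have a described report form, and no prompted, graded item records a non-serious skin reaction or application damage by leg, so harm cannot be compared systematically between paste and dry bandages

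*Protocol*

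**What the plan says.** Under Compression bandage selection procedure, the leg is the unit that is allocated: "one leg will be bandaged in 'paste' compression and one leg in 'dry' compression, through a process of randomisation".

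The section Reporting of safety events and device complaints states what may go wrong: "Anticipated risks can be associated to misuse (e.g. poor compression bandage application techniques) and allergy to the bandages components". It then turns to serious events: "In the very unlikely event that a Serious Adverse Event (SAE) has to be reported, a form has been devised". A definition of a serious event follows (death, life-threatening illness, permanent impairment, hospitalisation and similar). Nothing is said about how a non-serious event or a device complaint is recorded.

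The Appendix 3 clinical experience form is completed separately for the right and the left leg, with the bandage code circled. A typical item is "Has this bandage improved your skin irritation", answered Yes, No or N/a. Table 1 under Timeline schedules this form and the nurse application form at weeks 1, 4 and 8, and photographs of both legs at weeks 0, 1, 4 and 8.

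Under Criteria for Withdrawal/Discontinuation/exit, discomfort or intolerance to a bandage component ends the patient's participation. The reason for any withdrawal is recorded for the subject.

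**The concern.** The two risks that the protocol anticipates can both occur without meeting the definition of a serious event. A contact rash or a pressure mark are examples. The one event form described would miss them, so their capture depends on the other instruments.

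This matters for the study's own purpose. The Project summary says the inspiration came from patients who cannot tolerate compression. The Safety section accepts that bandage types may differ in how well they control symptoms such as itch. Appendix 1 collects eczema, psoriasis and other dermatitis at baseline, which are plausible markers of who reacts to which product. The Data analysis section expects new nursing guidance on bandage selection. If the structured leg-level items can register benefit but cannot separate harm from no effect, that guidance rests on a one-sided record. No later analysis can recover a distinction that the form did not collect.

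**Working it through.** The protocol gives no figure to reproduce on this point. The check is a count of items and a comparison of sections.

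**1. Per-leg clinical form (Appendix 3).** The count is from the right-leg version, because the end of the left-leg table is not fully legible in the text at hand.

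| Part | Closed items | Help or improvement | Other |
|---|---|---|---|
| Patient | 6 | 5 (pain, comfort, footwear and clothes, skin condition, irritation) | 1 (stayed in place) |
| Nurse | 6 | 4 (skin condition, irritation, healing, malodour) | 2 (washing, debridement) |
| Total | 12 | 5 + 4 = 9 | 1 + 2 = 3 |

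Items asking about a new or worsened reaction: 0 of 12. On each of the nine improvement items, a leg that did not change and a leg that got worse both give No.

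**2. Nurse application form (Appendix 3).** It has six items per leg: ease of application, ease of removal, neatness, ease of learning, ease of teaching, and whether the nurse likes the bandage. Items on skin harm: 0 of 6.

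**3. Pain and itch scales (Appendix 2).** These can show worsening and are taken at all four visits. Their printed instructions ask about leg pain and leg itching without saying which leg. With one paste and one dry leg in every patient, a single score cannot be assigned to a bandage.

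**4. Leg-level sources that remain.**
- Photographs: 4 visits × 2 legs × 40 patients = up to 320 leg-occasions. No grading is described.
- Clinical forms: 3 visits × 2 legs × 40 patients = up to 240, each with one patient comment field. The field invites remarks on experience and does not prompt for reactions.

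The 40 comes from Patient recruitment ("40 patients will be recruited for having bilateral leg ulceration").

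**5. Timing.** From "The duration of patient participation in the study is 8 weeks" and "compression bandages are changed 2-3 times per week", each leg has about 8 × 2 = 16 to 8 × 3 = 24 bandage changes. Against this, "The Research Nurse will visit each patient participant where they receive their treatment at Week 0, Week 1, Week 4, and Week 8" gives three visits after baseline. A reaction that appears and settles between visits has no prompted per-leg record.

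**6. Exit.** Table 1 has no exit assessment. A patient who stops between visits because of intolerance may leave without a further per-leg form. What is then certain to exist is a reason recorded for the subject, with no required leg or product.

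**The case against.** The strongest case on the other side has three parts.

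First, leg-level information does exist. A reader might infer that the questionnaires ask about nothing but improvement, or that non-serious reactions leave no trace by leg. The protocol does not support either reading. The clinical form also asks about staying in place, washing and debridement. Each leg has its own comment field next to a circled bandage code, and both legs are photographed four times. In a realist evaluation that brings sources together into themes, comments and photographs are working data. This stands, and it narrows the point to the lack of a prompted, graded record.

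Second, discomfort or intolerance leads to withdrawal with a recorded reason, so the group that reacts but stays in is smaller than it might seem. A reason that names zinc or calamine would point to the paste leg, since those components are described only for the paste products. This stands in part. A reason given simply as discomfort identifies neither leg, and the protocol does not require the leg to be stated.

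Third, the bandages are Class I CE-marked standard care, the study is considered low risk, and it states no safety objective. Restricting formal event reporting to serious events can be proportionate. That is a fair defence of the reporting procedure. It does not defend response options that merge unchanged with worse on the study's own comfort and skin items, nor a heading on device complaints with no content on them.

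**Conclusion.** The point holds as a weakness in data capture. The protocol names allergy and poor application as its anticipated risks, describes a form for serious events only, and gives no route for device complaints. None of the 12 closed items on the per-leg clinical form captures a non-serious reaction or application damage. Nine of the 12 cannot separate no effect from harm. The scales that can show worsening do not name a leg. Ungraded photographs and unprompted comments are the only direct per-leg sources, so a systematic comparison of harm between paste and dry legs is not possible.

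A reader might go further and infer that the study would declare an absence of safety events, or that a particular number of reactions would be missed. The protocol contains no such statement and gives no reaction rates, so neither inference is supported and no count of missed events is offered.

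The conclusion assumes that the Appendix 2 and 3 instruments are used as printed, and that no further event form exists beyond those the protocol describes.

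**What to change.** - Change the skin condition, irritation, pain and comfort items on the per-leg form from Yes/No/N-a to better / same / worse, keeping N/a.
- Add one line per leg at weeks 1, 4 and 8, and at exit for anyone who leaves early: local reaction or bandage-related damage (none / present), type, seriousness, bandage code, and any device complaint. Ask about the whole period since the last visit, so that reactions between visits are prompted for.
- Record the leg and bandage code with every withdrawal reason.
- State in the safety reporting section that non-serious events and device complaints are collected on this line, so that the text matches its heading.
- Report the results descriptively by leg and product in one table.

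None of this alters treatment or the rule for ending participation. The cost is a few more fields on forms already in use, slightly longer visits, a short exit record and one table. With 40 pairs the result describes harm by bandage and should not be presented as a test of a difference.

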# Data storage & archiving arrangements

The following data will be stored on NHS, password protected computers,

- personal addresses, postcodes and so forth will be used to contact patients and the GP surgery
- direct quotations from respondents will be used for publication
- digital photographs of their wound, consent will be sought for publication as well as for clinical reasons (standard care)
- storage of data: for data analysis.

Any paper files will be stored in a locked room (Research Nurse's office).

There is a need to retain patient identifiable data to organise data collection. This is to allow identification of patients and ability to approach potential participants and provide a Patient Information Sheet and consent form.

We will be using REDCap, which is a secure, web-based application to store data. Access will be restricted to named authorised individuals.

Nothing that could reveal participants identity will be disclosed outside of this project.

Personal data be stored or accessed for 3 months or less after the study has ended. The research data generated by the study will be held for 5 years.

# Dissemination of results and publication policy

Findings will be introduced in NuTH clinical practice, advancing knowledge translation. Impact will be maximised regionally and nationally, through the following presentation:

- (i) 2-3 international clinical conferences (2025).
- (ii) Regional wound care networks and the Shelford Tissue Viability Group.;
- (iii) 1-2 clinical academic journal articles. Open access fees for these papers have been included in the proposed funding to ensure they reach a wide audience and to ensure transparency of the research.

# **APPENDIX 1: BASELINE MEASURES**

To determine the demographics and characteristics of the patients, the following baseline data will be collated:

Patient details

- Age
- Sex
- BMI [BMI will be calculated using weighing scales if available or by using the Mid Upper Arm Circumference (MUAC) technique when weighing scale are not available].
- Mobility status: does not walk / walks with assistance (stick/frame) / walks without assistance.

Medical history and status:

- Significant comorbidities, including CEAP Clinical score, Peripheral Arterial Disease,
   Diabetes (type I, type II, +/- neuropathy), Heart failure, Eczema, Rheumatoid
   Arthritis, Psoriasis, Other dermatitis, , Multiple Sclerosis, Cancer
- Any previous leg ulcers within last 2 years.

Index leg and ulcer status

- Leg ulcer aetiology determining need for compression bandaging: Venous, Mixed, Skin tear, Management of oedema, Lymphoedema, other traumatic wounds.

Compression care characteristics

- Location of regular leg care: home (self-care) / home (district nurse)/Ambulatory care
- Frequency of care (change of compression bandaging: .... per week.
- Specific dressing used on wound.
  - o no
  - Yes, which?
- Skin care product used on index leg before application of compression bandaging.
  - o No
  - Yes, namely: Hydromol

Nursing teams and setting

Where and by whom is the patient been seen?
 (Which DN team; Ambulatory clinics)

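### Appendix 1 relies on an undefined index leg and has no right/left fields, so baseline aetiology, dressing and skin care are not assured for both randomised legs

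*Protocol*

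**What the plan says.** Under Compression bandage selection procedure, the protocol states that "one leg will be bandaged in 'paste' compression and one leg in 'dry' compression, through a process of randomisation". The Timeline section repeats that all legs are allocated: "Each leg will be randomised to either" one of the listed systems. The Patient recruitment section gives the number: "40 patients will be recruited for having bilateral leg ulceration", or in compression for prevention.

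Appendix 1 of the protocol, the list of baseline measures, is built differently. It has a heading "Index leg and ulcer status", under which the single item is "Leg ulcer aetiology determining need for compression bandaging". Among the care characteristics it asks for "Specific dressing used on wound", with no leg named, and for "Skin care product used on index leg before application of compression bandaging". No section defines the index leg, and no item in Appendix 1 has a right and a left entry.

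Other parts of the protocol do cover both legs. Table 1 schedules photographs of both legs at weeks 0, 1, 4 and 8. The questionnaires in Appendix 3 have separate right-leg and left-leg sections and are scheduled for weeks 1, 4 and 8.

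**The concern.** An index leg makes sense where one leg is studied and the other is not. Here both legs carry a study bandage, and the two legs of a patient carry different types. The protocol gives no rule by which a nurse could decide which leg is meant, and two nurses could decide differently. An entry made under this heading then belongs to the paste leg in some patients and to the dry leg in others, and nobody can tell which.

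This matters because the comparison is between the legs of one patient. Age, sex and BMI are shared by the two legs, so they cannot make the paste leg differ from the dry leg. Features of the leg can. Eligibility admits ulcerated legs and legs bandaged only for prevention, and the choice of full or reduced compression is said to depend on aetiology, among other things. The research question asks in what circumstances each type is selected, and the realist framework treats context as a main input. If the context of each leg is not recorded at baseline, no later analysis, however specified, can recover it.

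**Working it through.** The protocol gives no figure to reproduce on this point. The check sets the unit of randomisation beside the unit of the baseline record, item by item.

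**Unit of randomisation.** Each patient contributes two legs, and "one leg will be bandaged in 'paste' compression and one leg in 'dry' compression". With 40 patients this is 40 × 2 = 80 randomised legs.

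**Unit of the baseline record (Appendix 1).**

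| Baseline item | Leg named? | Right/left field? |
|---|---|---|
| Skin care product | Index leg, in the item itself | No |
| Aetiology | Index leg, through its heading only | No |
| Wound dressing | None | No |
| CEAP clinical score (listed with comorbidities) | None | No |
| Ulcer present or absent | No such item in the list | No |

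Only skin care is explicitly limited to one leg. On a literal reading it describes one leg per patient, so at most 40 of 80 legs. For aetiology the limit comes from the heading. For dressing, the text does not say whether one leg or both are meant.

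**Can an entry be linked to a bandage type?** Appendix 3 records the bandage code by side. A baseline entry can be linked to paste or dry only if it also carries a side. Appendix 1 carries none, so the link fails even for the leg that was recorded.

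**Do other records fill the gap?**

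- Photographs at week 0 cover both legs and show visible ulceration and skin condition. They do not state the aetiology, the dressing or the skin care product.
- The Appendix 3 items give bandage code (and so full or reduced compression), Hydromol washing and debridement for each leg. They start at week 1, after allocation, and do not ask about aetiology or dressing. They therefore do not replace baseline values.

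**Is this a matter of layout?** Appendix 3 prints every bandage-specific question twice, once for each leg. The authors split by leg where they meant to, and Appendix 1 contains no instruction to complete it once per leg.

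**The case against.** The strongest reply is that Appendix 1 is a list of what will be collated and not the data-entry form. The REDCap forms are not shown and may well have two columns. The analysis is descriptive and thematic, draws several data sources together, and plans no covariate adjustment. On that view this is a wording slip.

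Part of this stands. The form could be completed once per leg, and the study should not be held to the demands of a confirmatory trial. But the protocol does not say that it will be, and the term as written points the other way. A descriptive account of circumstances needs the leg's context as much as an adjusted model would.

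A reader might also infer more than the documents support:

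- *That one leg of each patient is unknown at baseline, or that 40 of 80 legs have no leg-level baseline.* Both legs are photographed at week 0, and only the skin care item is explicitly limited to one leg.
- *That leg-level features are the only ones that can modify the difference between paste and dry.* Patient-level factors such as age or mobility cannot be unbalanced between a patient's two legs, but they can change which bandage suits the patient, and Appendix 1 collects them.
- *That everything listed under comorbidity is shared by the two legs.* CEAP class, arterial disease and eczema can differ between legs.
- *That the gap makes chance imbalance between paste and dry legs likely.* The protocol does not say how many patients have legs that differ. The chance of imbalance under fair allocation is the same with or without a second column. What the column changes is whether an imbalance can be seen.

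**Conclusion.** The point holds in a limited form. Appendix 1 uses a term that is undefined and does not fit a design in which both legs of every patient are randomised to different bandages. As written, baseline skin care, and by its heading aetiology, is recorded for one unidentified leg, and dressing for no named leg. These three items are not assured for both legs and cannot be linked to the paste or the dry leg. Photographs and later questionnaires mitigate this only in part.

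The size is a count: three baseline items, with skin care covering at most 40 of 80 legs on a literal reading. That count assumes one entry per patient and would not apply if the form were in practice completed for each leg. No bias in any outcome has been shown, and sample size is unaffected. The change is worth making because baseline data not collected by leg cannot be recovered later.

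**What to change.** In Appendix 1, remove the term index leg and give separate right-leg and left-leg entries for aetiology, ulcer present or absent, dressing, skin care product and CEAP clinical class. State that these are completed before the allocation envelope is opened, and that each entry is linked by side to the allocated bandage. Add to the Data analysis section that they serve as leg-level context in the descriptive and thematic comparison of paste and dry legs.

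The cost is one extra column on the baseline form and a little more recording time at week 0. No visit, procedure, sample size or element of care changes. If the data-entry form already has both columns, the change is only to bring Appendix 1 into line with it.
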